### **3.2.3. Safety Endpoints**

The safety endpoints include the following parameters:

- Adverse events (AEs)
- Serious adverse events (SAEs)
- Condition/Diagnosis of AE

Start and stop date of the event

Serious event (yes or no)

Elements of the serious adverse events

- Results in Death
- Requires or prolongs Hospitalization
- Life-Threatening
- Congenital Anomaly/Birth Defect
- Results in permanent impairment of a body function or permanent damage to a body structure
- Necessitates medical or surgical intervention to preclude any one of the outcomes listed above

#### Severity of the event

- Mild
- Moderate
- Severe

#### Relationship to the study device

- Related
- Possibly Related
- Unrelated

#### Action taken

- None
- Treatment Stopped
- Treatment interrupted
- Unknown
- Concomitant Medication

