Thirty subjects in this study were evaluated for the effectiveness of the Provant Therapy System in the treatment of post-surgical pain after back surgery. Provant treatment twice daily for 45 days was associated with improved pain scores, improved overall well-being, improved physical function, and reduced analgesic consumption, especially in subjects who had undergone a discectomy.

The purpose of the current study is to confirm the findings of pain relief observed in patients receiving treatment with Provant in a “real-world”, post-market setting. Data from this study may be combined with other studies conducted in the post-market setting, i.e., in a patient registry.

II. STUDY OBJECTIVES

This study is designed to provide post-market evidence of the safety and effectiveness of the Provant Therapy System for improving pain and edema in subjects with multiple pain etiologies.

III. STUDY DESIGN

A. Study Design

The study is an open-label, non-controlled study of the safety and effectiveness of investigator determined Provant therapy in subjects with pain and/or edema from various pain etiologies.

B. Efficacy Assessments

Outcome measures of response to treatment with Provant will be determined based on the location of the subject's treatment area. Protocol required assessments will include baseline and interim / end of treatment visit and 3-month follow-up (post-treatment) pain scores using an 11-point numeric pain rating scale (NPRS), and a Clinical Global Impression – Global Improvement (CGI-I) Scale and a Patient Global Impression of Change (PGIC) Scale. All outcome measures used in the investigator's standard of practice are non-invasive assessments, e.g., pain scores, SF-36, ankle-foot scales, oxygen perfusion (MOXY), and diaries with some subjects.

C. Safety Evaluation

All observed and reported adverse effects will be recorded by the research staff. Start dates, end dates, frequency, severity of the event, any treatment required to treat the event, and the investigator's judgment on causality and relationship to the device will be assessed for each AE. Any AE occurring after the signing of the informed consent form will be recorded. Only those AEs occurring after initiation of the first treatment with the study device will be considered treatment-emergent AEs.

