| Mild: | The event is transient (<48 hours) or causes mild discomfort; no medical intervention/therapy is required |
| Moderate: | The event results in mild to moderate limitation in activity – some assistance may be needed; no or minimal medical intervention/therapy is required |

Severe: The event results in marked limitation in activity, assistance is usually required; medical intervention/therapy is required and hospitalization is possible

Each AE will also be independently judged by the investigator in terms of seriousness. A serious adverse event (SAE) is defined as any untoward medical occurrence that:

- Results in death, or
- Is life-threatening,

Note: The term “life-threatening” in the definition of “serious” refers to an event in which the subject was at risk of death at the time of the event; it does not refer to an event which hypothetically might have caused death if it were more severe.

- Requires inpatient hospitalization or prolongation of existing hospitalization,
- Results in permanent impairment of a body function or permanent damage to a body structure,
- Is a congenital anomaly/birth defect,
- Necessitates medical or surgical intervention to preclude any one of the outcomes listed in this definition.

All SAEs must be reported *immediately* (within 24 hours of knowledge of the event) by telephone and fax to the following:

Sponsor Medical Contact – [name]; Regenesi Biomedical Inc.

[contact]; [contact]; [contact]

The investigator will follow up with a written description of the SAE submitted to the sponsor within 3 days, including the results of the SAE investigation and any treatment(s) provided.

All adverse events will be followed until resolution or until the investigator assesses the subject’s status has returned to normal.

B. Anticipated Adverse Device Effects Associated with Provant

Anticipated adverse events associated with Provant, reported at least once since market launch in 2004, are as follows:

- Device fails to operate
- Warmth or burning at treatment site
- Skin reaction at treatment site (tingling, pins-and-needles, rash, blisters, swelling, dry skin, redness, numbness, sensation of warmth)
- Increased bleeding at surgical site
- Chilliness
- Headache
- Malaise
- Nausea

- Abdominal or chest wall discomfort
- Muscle cramps
- Failure to reduce pain or an increase in pain
- Metallic taste in mouth
- Exacerbation of tinnitus
- Stiffness
- Weakness
- Dizziness/lightheadedness

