#### 11.1.2. Summaries of Adverse Events

All summaries of AEs will be based on treatment-emergent AEs and presented using the Level 3 table designs. Adverse events will be mapped to preferred terms and body systems using the Medical Dictionary for Regulatory Activities (MedDRA) coding dictionary version 18.1. The number and percentage of subjects experiencing AEs will be summarized by system organ class and preferred term. Summaries by maximum severity and relationship to the study device will also be provided. Serious adverse events and AEs leading to discontinuation from the study will be presented by system organ class and preferred term.

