#### **11.1.2.4. Summary of Adverse Events Leading to Discontinuation**

Results will be presented in Table 14.3.1.4 entitled *Summary of Adverse Events Leading to Discontinuation of Treatment with the Study Device* by System Organ Class and Preferred Term (ITT / Safety Population). The structure of the table will follow Table 14.3.1.1. Listing 16.2.6.3 entitled *Adverse Events Leading to Discontinuation of Treatment* will display all treatment-emergent AEs resulting in an action taken of “Discontinued”.

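### The AE 'Action taken' item mixes device action with drug treatment, and the discontinuation listing filters on a code the item does not contain, so AEs that stopped the device can be missed

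*SAP*

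**What the plan says.** SAP 3.2.3 (Safety Endpoints) lists five options under 'Action taken': None, "Treatment Stopped", "Treatment interrupted", Unknown and "Concomitant Medication". It gives no rule on multiple answers and no order of priority.

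SAP 11.1.2.4 plans two outputs on AEs leading to discontinuation.
- For Listing 16.2.6.3 it gives a filter: the listing "will display all treatment-emergent AEs resulting in an action taken of" 'Discontinued'.
- For Table 14.3.1.4 it gives a title, which refers to discontinuing treatment with the device, and a layout: "The structure of the table will follow Table 14.3.1.1". It names no selection variable for the table.

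The overview in SAP 11.1.2 describes the output differently: "AEs leading to discontinuation from the study will be presented by system organ class and preferred term".

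Drug treatment of an AE is also captured elsewhere. The concomitant medication fields in SAP 3.2.3 include 'CM for AE', and Listing 16.2.14 (SAP 11.2) shows whether a medication was used for an AE. Protocol III.C requires each AE assessment to cover "any treatment required to treat the event" and commits to displaying AEs that lead to discontinuation.

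**The concern.** What was done with the device and what was given for the event are two separate questions, and one AE can have an answer to both. When they share one item, whether an AE is recorded as having stopped the device may depend on which answer the site prefers. The output meant to show device-stopping AEs is selected on that item, and the selecting value is not one of its codes.

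AEs leading to discontinuation are among the few safety results that the protocol and SAP name specifically. In an uncontrolled study with a safety objective, a count that can err only downwards, and only among events that also received a drug, deserves a clear definition.

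**Working it through.** No arithmetic figure in the plan depends on this point, so the check sets the sections side by side.

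**1. What each code describes (SAP 3.2.3)**

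| Code | Describes the device | Describes treatment of the event |
|---|---|---|
| None | yes | unclear |
| Treatment Stopped | yes | no |
| Treatment interrupted | yes | no |
| Unknown | yes | unclear |
| Concomitant Medication | no | yes |

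The last code is not an alternative to the others, because it can be true together with a stop or an interruption.

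**2. The filter read literally (SAP 11.1.2.4).** The value 'Discontinued' is compared with the five codes above and matches none of them. Even an AE coded as device stopped is not selected. This follows from the text without any assumption about the form.

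**3. The filter read as device stopped.** The result now depends on the response format, which the SAP does not state.
- *Several answers allowed, all that apply ticked:* the AE carries both codes and is selected. Nothing is lost, provided that any tick for a stopped device counts.
- *One answer only:* an AE with both a stop and a drug must take one code. If the site picks the drug option, the AE is not selected.

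A single answer is the more natural reading. The list contains None and Unknown, which exclude other answers, and the neighbouring items (severity, relationship, frequency, outcome) each take one answer. It is not certain, because the elements of a serious AE in the same section are listed in the same style and can occur together.

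**4. The table.** The filter is stated for the listing only. Section 11.1.2.4 names no other variable, so Table 14.3.1.4 probably uses the same selection, but that is an inference. SAP 11.1.2 also speaks of leaving the study, whereas the titles in 11.1.2.4 speak of stopping treatment. These are different events: under Protocol V, a subject who stops the device is still sought for the End of Treatment assessments.

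**5. Size.** Let D be the number of AEs that stopped the device, f the share of these that also received a drug, and s the share of those coded only under the drug option. With the filter read as device stopped:

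AEs missed = D × f × s

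- s = 0 (several answers allowed and all ticked): 0 missed.
- s = 1 (one answer, always the drug option): D × f missed, which is the maximum.

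The documents give none of D, f or s, so only the bounds 0 to D × f can be stated. The effect on subjects is no larger than the effect on AEs. The layout of Table 14.3.1.1 counts a subject once per system organ class and once per preferred term, so a subject with another correctly coded event in the same row is still counted.

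**6. Direction.** The mixed item can remove a device stop from the selection but cannot add a false one. Any error from it is therefore an undercount.

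**The case against.** The strongest reply is that nothing in the SAP makes the item single-choice. The form is not in the documents, and the filter wording can equally mean that this action is among those ticked. That stands, and it is why the loss under the second reading of the filter is conditional.

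A programmer would also probably read 'Discontinued' as the stopped code, so an empty listing is unlikely in practice. That is fair, but the SAP should not leave the mapping to be guessed, and the mapping alone does not recover an AE coded under the drug option.

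There are also backstops. A miscoded AE stays in all the other AE tables and in Listing 16.2.12, its drug appears in Listing 16.2.14, and Table 14.1.1 is to cover reasons for early study termination. These allow a cross-check but do not replace the output: Table 14.1.1 concerns leaving the study and is not described as identifying the AE that stopped the device.

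Two stronger readings are tempting and are not supported.
- A reader might infer that such AEs certainly drop out of Table 14.3.1.4, or that a percentage undercount can be given. The table has no stated filter, and the documents contain no AE rate or coding share from which a percentage could follow.
- A reader might infer from the protocol's definition of a severe AE ("medical intervention/therapy is required and hospitalization is possible") that severe events always receive a drug and so are the ones most often miscoded. Intervention or therapy need not be a drug, so the definition does not establish this.

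**Conclusion.** The point holds as a minor defect. Two things are certain from the text. The item mixes device action with drug treatment without a response rule, and the listing filter names a value that is not among the item's codes. It is conditional that an AE with both actions is missed: this needs a single-answer form, or incomplete ticking, and a site that chooses the drug option. That the table is affected in the same way as the listing is probable but not stated.

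The loss lies between zero and the number of device-stopping AEs that also received a drug, always as an undercount, and cannot be quantified further. One descriptive safety output is affected. No hypothesis test or sample size depends on it.

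**What to change.** 1. Split the item. Record 'Action taken with study device' as None / Treatment interrupted / Treatment stopped / Unknown, and record drug treatment of the AE as a separate yes/no taken from the existing 'CM for AE' field. If the form already accepts several answers, it is enough to state in the SAP that any tick for a stopped device counts, whatever else is ticked.
2. In SAP 11.1.2.4, define both Table 14.3.1.4 and Listing 16.2.6.3 as treatment-emergent AEs with the device action 'Treatment Stopped', replacing 'Discontinued'. Align SAP 11.1.2, so that it is clear whether the output concerns stopping treatment or leaving the study.
3. Query AEs already coded only under the drug option to establish whether the device was also stopped, and cross-check against the early-termination reasons in Table 14.1.1.

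The cost is a few sentences in the SAP, one pick-list edit if the form is single-choice, and a small number of queries. No new assessments of subjects are needed.

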#### Frequency

- Single, continuous episode
- Recurrent / Intermittent

#### Outcome of the Event

- Recovered
- Resolved with residual effects
- Death
- Unknown
- Ongoing at study end

#### Concomitant medications

- Medication Name
- Indication / Reason for Use (verbatim)
- Start date
- Stop date
- CM for AE
- Dose
- Units

- Frequency
- Route
- Ongoing

## **4. STUDY OVERVIEW**

### **4.1. Study Design**

This is an open-label, non-controlled trial in subjects with various pain etiologies at multiple centers in the US. Up to 200 subjects will be enrolled. Eligible subjects will include those  $\geq 22$  years of age that have been deemed appropriate for treatment with Provant by the study investigator (prescriber). Subjects will treat based on the treatment prescribed (location, frequency, duration) by the study investigator. Data from assessments administered as part of standard of practice will be obtained at baseline and, at a minimum, at the end of treatment. If the investigator administers additional assessments during the course of treatment, the data will be collected. Safety will be assessed during office visits and through review of AE reports and concomitant treatments and medications. All concomitant drug or non-drug treatments used during the study will be recorded.

Subjects will be instructed in the use of the device and will self-treat as prescribed by the study investigator. As part of the investigator's standard of practice, subjects may be provided with a patient reported outcome form(s) for capturing their daily pain scores, which may include a 10 point numerical pain score scale, or other patient-reported outcomes related to the pain etiology. Subjects will document outcomes as instructed by the site at the Enrollment Visit.

After up to 20 weeks of treatment, the subject will return to the clinic for a final assessment. Adverse events and changes in concomitant medications will be collected.

### **4.2. Study Device**

The study device is the Provant® Therapy System which delivers Pulsed Electromagnetic Field (PEMF) energy therapy. Each device will be identified by a unique serial number.

### **4.3. Sample Size Justification**

There is no formal basis for the sample size of 200 subjects. The intent of this clinical investigation is to record real-world use and the practice pattern of this approved medical device.

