CLINICAL STUDY PROTOCOL

Study Title: **An Open-Label, Non-Controlled Study to Evaluate Outcomes of Pulsed Electromagnetic Field (PEMF) Therapy in Subjects with Various Pain Etiologies**

Protocol Number: RBI.2015.005

Version: B

Phase: Post-Market

Sponsor: Regenesis Biomedical, Inc.
[name]
[name]

Medical Contact: [name]
Vice President, Clinical Business and Education
Regenesis Biomedical, Inc.

Final Approval Date: 18 January 2017

PROTOCOL SIGNATURE PAGE – SPONSOR

Study Title: **An Open-Label, Non-Controlled Study to Evaluate Outcomes of Pulsed Electromagnetic Field (PEMF) Therapy in Subjects with Various Pain Etiologies**

Protocol Number: RBI.2015.005

Version: B

The undersigned acknowledges that he/she has received and read Protocol RBI.2015.005, Version B, dated 18 January 2017.

Sponsor Representatives	Signature	Date
[name] Vice President, Clinical Business and Education		
[name] Director Clinical Research		

PROTOCOL SIGNATURE PAGE – Principal Investigator

Study Title: **An Open-Label, Non-Controlled Study to Evaluate Outcomes of Pulsed Electromagnetic Field (PEMF) Therapy in Subjects with Various Pain Etiologies**

Protocol Number: RBI.2015.005

Version: B

The undersigned acknowledges that he/she has received and read Protocol RBI.2015.005, Version B, dated 18 January 2017.

Principal Investigator	Signature	Date

DOCUMENT REVISION HISTORY		
	Date	Summary of changes
Version A	01/11/2016	Original document
Version B	1/18/2017	Updated to include the Numeric Pain Rating Scale (NPRS), Clinical Global Impression – Global Improvement (CGI-I) Scale, Patient Global Impression of Change (PGIC) and 3-Month follow-up and signature line for [name].

Study Synopsis

Study Title	An Open-Label, Non-Controlled Study to Evaluate Outcomes of Pulsed Electromagnetic Field (PEMF) Therapy in Subjects with Various Pain Etiologies
Protocol Number	RBI.2015.005
Name of Study Device	Provant [®] Therapy System
Phase of Development	Post-Market
Objective	To obtain data on the safety and effectiveness of PEMF treatment in patients with various pain etiologies. Data from enrolled patients will contribute to a patient registry on the post-market use of Provant.
Number of Subjects	Up to 300 subjects will be enrolled.

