Demographic and subject characteristics will be summarized using descriptive statistics. Assessments that are measured on a continuous scale will be summarized descriptively using the mean, standard deviation, median, minimum, and maximum value by time. Variables that are measured on a categorical scale will be summarized as a proportion of the population.

The change from baseline will be summarized for effectiveness outcome assessments in common between subjects/sites and 95% confidence intervals constructed.

Adverse events will be summarized using MedDRA categories and by severity and relationship. Concomitant medications will be summarized by WHODrug categories.

C. Adverse Events

All adverse events will be coded according to Medical Dictionary for Regulatory Activities (MedDRA). Safety assessments will include treatment-emergent adverse events (TEAEs; adverse events that occur in subjects who undergo treatment). Subjects with TEAEs will be summarized with frequencies and percentages by system organ class and preferred term, severity, and relationship to treatment for each treatment group. Treatment-related adverse events will be defined as adverse events with investigator assessment of related or possibly related. In summaries of TEAEs by severity and relationship to study device, subjects reporting multiple episodes will be counted once under the worst severity and the strongest relationship, respectively. Serious Adverse Events will also be presented by relationship to treatment.

The number of subjects with at least one adverse event will be tabulated. The number of adverse events will also be tabulated. The number of subjects and the number of adverse events will be tabulated by severity and relationship.

D. Sample Size

This is an open-label, non-controlled study with no formal hypothesis testing planned. It is anticipated that up to 300 subjects will be enrolled in this study. Data from this study will be included in a patient registry. The statistical analysis plan for the patient registry will fully describe the methods used to evaluate data from this study.

VII. INFORMED CONSENT

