### **4.4. Estimated Duration of Subject Participation and Follow-up**

Subjects will be followed for up to 20 weeks (including the screening period). If a subject completes the study with an ongoing AE, the site will continue to follow up with the subject for 30 days from the study completion date, until resolution is reached and documented. If, after 30 days, the AE is still continuing but not assessed as serious, the outcome will be recorded as ongoing and no further follow-up will be necessary. If a subject completes the study with an ongoing SAE, the subject will be followed until resolution or stabilization (i.e., the AE returns to baseline, can be attributed to agents other than the study device, or to factors unrelated to the study conduct; or no further follow-up is deemed necessary by the Investigator or it becomes unlikely that any additional information can be obtained).

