#### **4.5. Interim Analysis**

An administrative extract of the data on September 2, 2016 will be used to tabulate the data for the post-operative patients. This tabulation is being prepared for a regulatory filing and does not constitute a formal analysis.

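### The SAP's final pain tables admit subjects whom protocol VI.A excludes from End of Treatment analyses, and the 3-month NPRS has no summary; size, duration and confidence intervals also do not match the protocol

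*SAP*

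**What the plan says.** **Final pain result.** Protocol VI.A leaves subjects who do not attend the End of Treatment Visit out of the End of Treatment analyses. The synopsis likewise limits each efficacy summary to subjects evaluated at that time point. SAP 10.3.1 and the Level 2 Final Score rows in SAP 7 instead use the last value recorded for each subject, with no restriction to a visit. SAP 7.2 says that missing values are not imputed and that last recorded observations will be tabulated.

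**3-month NPRS.** The protocol requires it (synopsis, IV.F, and the last column of Appendix A). The SAP schedule (section 5) stops at the End of Treatment Visit, and none of Tables 14.4.1.1 to 14.4.2.3 is for the call.

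**Size.** SAP 4.1: "Up to 200 subjects will be enrolled". SAP 4.3: "There is no formal basis for the sample size of 200 subjects". Protocol VI.D: "It is anticipated that up to 300 subjects will be enrolled in this study".

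**Duration.** SAP 4.1: "After up to 20 weeks of treatment, the subject will return to the clinic for a final assessment". SAP 4.4 caps follow-up at 20 weeks and counts screening inside that limit.

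**Intervals.** Protocol VI.B: "The change from baseline will be summarized for effectiveness outcome assessments in common between subjects/sites and 95% confidence intervals constructed". No SAP display or convention lists a confidence interval.

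**Global scales.** The protocol requires CGI-I and PGIC. The SAP names neither.

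**The concern.** Protocol VI makes its own statistical section the basis for the SAP, and SAP 2 makes this SAP the plan for the study report, so the two should agree on who is counted and at which time points.

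Followed as written, the SAP body yields no pain table that applies the VI.A rule. It also has no rule for the only outcome measured after treatment ends. If the call does not count as part of the study, its score is in no summary. If it does count, it replaces the End of Treatment score in the Final Score, and on-treatment and post-treatment pain are merged. Left open, the definition of the final score would be settled after the data are in.

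The likely cause of part of this is timing. SAP 4.5 speaks of a future event: "An administrative extract of the data on September 2, 2016 will be used to tabulate the data for the post-operative patients". Protocol Version B carries "Final Approval Date: 18 January 2017". The SAP's own date is not visible in the text available, so this is an inference.

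**Working it through.** **1. Size.** There is no calculation to reproduce: neither document gives an effect size, SD, power or margin, and no formal test is planned. The gap in ceilings is 300 − 200 = 100 subjects. If both ceilings were reached, a confidence interval at 300 would be √(200/300) = 0.816 times as wide as at 200. Nothing else follows from it.

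**2. Duration.** Inputs: screening window up to 14 days, treatment up to 20 weeks, call three months after the End of Treatment Visit (taken as 13 weeks = 91 days, an assumption).
- SAP 4.4 cap: 20 × 7 = 140 days.
- SAP 4.1 plus screening: 14 + 140 = 154 days, which is 14 over the SAP's own cap.
- Protocol: 14 + 140 + 91 = 245 days (35 weeks), which is 105 days (15 weeks) over.
- With screening and enrollment on one day, which both documents allow, SAP 4.1 gives 140 days and meets the cap. The protocol gives 140 + 91 = 231 days, still 91 over.

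**3. Who is in the final mean.** Let *A* be the mean change among attenders of the End of Treatment Visit, *m* the share of subjects in the final table who missed that visit but have an interim score, and *D* their mean change minus *A*. With the call excluded:

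last-recorded mean = (1 − m)A + m(A + D) = A + mD.

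The shift is mD, which is zero if nobody misses the visit or if non-attenders fare alike. The documents give neither *m* nor *D*. Assumed ranges only:

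| m | subjects, of 300 | D = −2 | D = −1 | D = 0 | D = +1 | D = +2 |
|---|---|---|---|---|---|---|
| 5% | 15 | −0.10 | −0.05 | 0 | +0.05 | +0.10 |
| 10% | 30 | −0.20 | −0.10 | 0 | +0.10 | +0.20 |
| 20% | 60 | −0.40 | −0.20 | 0 | +0.20 | +0.40 |

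Positive values mean less improvement. The change in denominator is certain once *m* > 0; the change in the mean is not.

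**4. Where the 3-month score goes.** SAP 3.2.2 places the post-baseline pain score under interim and End of Treatment visits, which favours the reading that the call score is in no table. The Final Score rows refer to the study as a whole, which allows the other reading. Under that reading the shift is f × d, where *f* is the share with a call score and *d* the mean change after treatment. With assumed f = 0.7 and d from −1 to +1 it runs from −0.7 to +0.7, and is 0 if pain is stable. No SAP rule chooses between the readings.

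**5. Statistics shown.** The Level 2 rows list N, mean, SD, median, range and inter-quartile range, for raw scores and for change. The conventions in SAP 7 list a similar set. Neither contains an interval. The change rows cannot apply to CGI-I or PGIC, because Appendix A note 3 says these are not done at baseline.

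**The case against.** **The size figures are compatible ceilings.** Enrolling 200 or fewer satisfies both documents. This stands: a reader might infer a loss of power, but there is no test to lose power for.

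**The SAP is simply one protocol version behind.** This explains part of it. The Version B revision history lists the NPRS, CGI-I, PGIC and the 3-month follow-up. It does not list size, the End of Treatment rule or confidence intervals, so a reader who ascribes every mismatch to Version B goes further than the text allows.

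**The last-recorded tabulation is announced, and few subjects are affected.** SAP 7.2 does announce it, and VI.A also says that effectiveness summaries cover all treated subjects. With the call excluded, attenders have the same value under both rules, and the protocol asks for final assessments at discontinuation. All true, so the tabulation may stay. What is missing is a table that applies VI.A.

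**The 3-month score will still be reported.** One might infer that it goes unreported. SAP 7 says all study data will be listed, so what it lacks is a summary.

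**CGI-I might be averaged with its zero code for entries not assessed.** The documents do not support that inference. SAP 10.2 and 10.3 call for counts and percentages for categorical variables, SAP 7 separates not-performed from missing data, and the Level 2 display is offered as an example layout.

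**Other documents may fill the gaps.** The registry SAP cited in protocol VI.D and the table index cited in SAP 13 are not shown. They could hold a 3-month table or the intervals. They would not correct the text of SAP 4.1, 4.3, 4.4 and 5.

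**Conclusion.** The point holds as an alignment defect with two substantive parts: the SAP body has no pain table that follows VI.A, and no summary or allocation rule for the 3-month NPRS. These decide who is in the final pain result and whether the only post-treatment outcome is summarised.

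The rest is lesser. The 100-subject difference is administrative. SAP 4.4 conflicts with SAP 4.1 by up to 14 days when the full screening window is used, and with the protocol by up to 105 days for a subject treated for the full 20 weeks. On intervals the SAP is silent rather than contradictory, and the protocol's promise covers only assessments in common between subjects or sites, so a reader should not infer that every change score needs one.

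No type I error or power is affected. The size of any shift in the mean is unknown and may be zero; every shift shown rests on assumed rates and differences. The conclusions about missing tables rest on the SAP body alone.

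**What to change.** Amend the SAP to:
- add an End of Treatment Visit pain table restricted to attenders, as VI.A requires;
- keep the last-recorded tabulation of SAP 7.2 under its own label, with a cut-off that excludes the 3-month call;
- add a separate summary of the 3-month NPRS and its change from baseline;
- show 95% confidence intervals for change from baseline in the assessments covered by VI.B;
- name CGI-I and PGIC and tabulate them as category counts and percentages, with no change-from-baseline row;
- bring the enrollment figure, follow-up duration and schedule in SAP 4.1, 4.3, 4.4 and 5 into line with the protocol.

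The cost is one SAP amendment and the table programming. The protocol already collects the data, so no visit or subject is added. It should be done before the final tables are run, so that the final score is defined in advance.
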